3 INVESTIGATIONAL DRUG

3.1 CLONIDINE

Clonidine is a selective alpha 2-adrenoceptor agonist used preoperatively for its intrinsic analgesic, sedative and anxiolytic effects. The mechanism of action of Clonidine is thought to not only exert its sedative action via the stimulation of alpha 2 receptors in locus coeruleus, which was responsible for sleep and arousal [20]. When used intrathecally, the primary mechanism responsible for the beneficial effect of alpha-2 agonists is binding to alpha-2 receptors in the dorsal horn of the spinal cord. Clonidine may also interfere with the repolarization process (the hyperpolarization-activated cation current) in the spinal nerves optimizing the endogenous inhibitory descending pain response [21]. Clinically, Clonidine has been extensively studied in pediatric anesthesia, particularly when administered caudally or intrathecally with a local anesthetic agent [22-24]. It also can be used orally or intravenously to decrease the consumption of propofol sedation [25,26], which is quite relevant for this study as propofol is the analgesic of choice for Total IntraVenous Anesthesia (TIVA) required for spinal cord monitoring.

[figure not shown]
More specifically the use of Intrathecal Clonidine has been demonstrated to prolonged analgesia and decreased morphine consumption postoperatively [27]. Both epidural and intravenous routes achieve postoperative analgesia, but the overall dose required of Clonidine was lower by the epidural route [28].

The administration of 1ug/kg intrathecal Clonidine has been shown to improve the efficacy of postoperative sedation and analgesia and prolong time to first rescue analgesia after surgery and reduce the requirements of propofol for intraoperative sedation [29].

4 PRELIMINARY DATA AND CLINICAL DATA

In a previous study, we have demonstrated that presence of pain before surgery was the best predictor of pain intensity after surgery in Adolescent Idiopathic Scoliosis (AIS) patients undergoing surgery [30]. Pain before surgery was reported by 48% of the cohort (n=50) (Figure 1). We also demonstrated that intensity of pain in the first days after surgery was associated with pain intensity weeks after surgery, thus demonstrating the clinical need to improve preoperative and acute pain management in order to minimize long-term consequences.

Figure 1. Patients reporting preoperative pain had greater postoperative pain intensity levels during the first postoperative 24 hours (POD1, $r=0.47$, $p=0.001$) (A), the second 24 hours (POD2, $r=0.35$, $p=0.025$) (B) and at follow-up appointment (4-6 weeks after surgery, $r=0.50$, $p<0.001$) (C). The pain intensity during POD1 was also predictive of the pain intensity during POD2 ($r=0.74$, $p<0.001$) (D) and at follow-up (6 weeks post-surgery, $r=0.43$, $p=0.005$) (E) (Ferland et al. 2016, PMID: 26852092).

In the same cohort, we also quantified neurotransmitters known to be related to pain. The preoperative plasma levels of norepinephrine metabolite metanephrine concentrations revealed to be associated with the postoperative pain intensity (Figure 3). Although preliminary, these results suggested that preoperative inter-individual differences, could explain postoperative pain trajectories.

[figure not shown]
[figure not shown]

[figure not shown]
Figure 2. Preoperative monoaminergic levels on postoperative pain intensity. The preoperative metanephrine plasmatic levels of AIS patients scheduled for surgery. Patients who reported greater pain intensity at 6 weeks after surgery had higher metanephrine plasmatic levels before surgery (n=50, $P<0.001$) (Ferland et al., manuscript in preparation).

In the largest study to examine longitudinal pediatric pain trajectories after spine surgery, Sieberg et al proposed perioperative trajectories of pain experience may be better explained by changes in the central pain modulation rather than in the surgical stimulus itself (Figure 3).

Figure 3. Five empirically derived pain trajectories were identified in a subset of patients with Adolescent Idiopathic Scoliosis (n = 77) (Sieberg CB et al., 2013, PMID: 24290449). Illustrating that patients respond differently to painful surgical stimuli as well as to standardized analgesia regimen. Our hypothesis is that one can identify preoperatively (using QST and or biomarkers) how patient will respond to pain postoperatively.

A key mechanism of the central pain modulation is the endogenous analgesia system [31]. Efficacy of inhibitory mechanisms can be tested by using the response of conditioned pain modulation (CPM). It is a powerful analgesic mechanism illustrated when a painful stimulus is inhibited by a second painful stimulus delivered at a different body location [32]. In a previous study, we reported the CPM distribution in healthy subjects having no pain condition at the moment of the measurements (Figure 5). Approximately half (42%) of the healthy subjects had a pain reduction of 10% (minimal clinical change) or more [33].

Poor CPM, or lack of reduction in pain during the presence of the conditioning stimuli was reported in patients with various chronic pain disorders [34-36]. The risk of developing chronic pain following surgical procedure is related to lower efficacy of CPM in humans [37,19]. Although used to assess perioperative efficacy of endogenous inhibition in adults, the use of CPM during the perioperative period surrounding a surgery in pediatric patients has not yet been evaluated.

Considering that the modulatory effects of the endogenous inhibition are largely mediated by descending serotonergic and noradrenergic pathways [38,39], we further studied

catecholamines as possible biomarkers of pain. Multivariate analyses of perioperative catecholamines levels revealed preoperative plasmatic concentrations of norepinephrine (NE) and normetanephrine (NME) and the cerebrospinal fluid (CSF) concentration of NE were significantly correlated with the presence of pain six weeks after surgery ($r = 0.50, 0.49$ and 0.50 respectively, $p < 0.002$), (Figure 6) [30]. These results support the evidence for a potential role of the endogenous inhibitory mechanism and catecholamine levels in predicting postoperative pain intensity and provide clues as to a mechanism-based pre-analgesic approach to perioperative pain management.

Catecholamines	Pain	Plasma (n=50)	CSF (n=38)
NE	Preoperative	$r = .05, p = 0.70$	$r = .11, p = 0.51$
	POD1	$r = .06, p = 0.70$	$r = .30, p = 0.07$
	POD2	$r = .02, p = 0.91$	$r = .18, p = 0.28$
	6 weeks	$r = .48, p = 0.0004$	$r = .50, p = 0.002$
NME	Preoperative	$r = .06, p = 0.68$	$r = .008, p = 0.96$
	POD1	$r = .21, p = 0.14$	$r = -.18, p = 0.27$
	POD2	$r = .13, p = 0.39$	$r = -.26, p = 0.13$
	6 weeks	$r = .50, p = 0.0003$	$r = .25, p = 0.13$

Figure 5. Associations between preoperative catecholamine levels and pain. NE: norepinephrine; NME: normetanephrine; CSF: cerebrospinal fluid; POD1: postoperative day 1; POD2: postoperative day 2. (Spearman correlations).

Considering the clinical success of pharmacological interventions that enhance spinal noradrenergic activity in the treatment of chronic pain states [38,40,41], as well as the evidence that optimizing the inhibitory descending endogenous signaling may determine the recovery from hypersensitivity after surgery [42], we believe we are close to achieving a novel personalized pain management approach to perioperative pain in orthopedic surgery by introducing pre-emptive analgesia in the form of an alpha-2 inhibitor. Similarly, You et al. demonstrated in an animal model that pre-emptive analgesia optimizing the endogenous inhibitory mechanism by the use of an alpha-2 adrenergic receptor had better pain control than Fentanyl in preventing mechanical hyperalgesia in the context of surgical insult [43].

Spinal Clonidine before surgery and oral / IV Clonidine after surgery have been extensively utilized in the perioperative setting. Our proposal is to pre-operatively select patients who we believe Clonidine will improve significantly their pre-operative course.

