8 STUDY DESIGN/PROCEDURES

8.1 GENERAL DESIGN

This study is a randomized-controlled double-blind study. All consecutive female patients who come to the Shriners Hospital for Children – Canada, and who meet the Inclusion/exclusion criteria will be invited to participate in the study throughout the study's specified recruitment period to avoid selection bias.

Subjects will be expected to participate for 6 months. Subjects will be assessed for eligibility, consented and enrolled if they meet all criteria. They will undergo a baseline visit prior to surgery. CPM testing results will determine the subjects to be in one of two arms – 1) Sub-optimal endogenous inhibitory response or 2) Optimal endogenous inhibitory response. The subjects in each of these two groups will be randomized to either be treated with Clonidine arm or the placebo arm. Subjects will be followed in-hospital, and at 6 weeks and 6 months.

All clinicians and researchers involved in the recruitment, consent, data collection, experimental procedures and data analysis will remain blinded to study group allocation for the duration of the study. Blinding will be maintained until the end of statistical analysis, unless un-blinding is required. Although the study will be conducted at the Shriners Hospital for Children – Canada, including analysis of all specimens, the Pharmacy of the McGill University Health Centre will manage the randomization, blinding of medication/placebo as well as the distribution of the medication/placebo on the day of surgery and for 5 days post-operatively.

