16.3 SAMPLE SIZE DETERMINATION AND POWER / ACCRUAL RATE

The sample size was calculated for the primary outcome (average pain intensity over the past 7 days six months after surgery). Assuming that a 2-point change on the 0–10 pain intensity scale constitutes a clinically meaningful difference [74,76], a standard deviation of 2.0 units, a study design with 3 repeated measurements having a compound symmetry covariance matrix, a power of 90%, a two-sided alpha level of 0.05 and a conservative autocorrelation coefficient (rho) of one,

a minimum of 22 patients per comparison group is required. To prevent reduced power because of patient loss to follow-up and to minimize confounding effects, 35 patients per group will be enrolled (35 x 4 groups = 150 patients in total).

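### Section 16.3 states 35 patients in each of four groups, but CPM class is observed rather than assigned, so the design does not fix the group sizes and one power figure does not describe every comparison

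*Combined protocol and SAP*

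**What the plan says.** Section 16.3 derives the sample size from a 2-point difference that "constitutes a clinically meaningful difference", with "a standard deviation of 2.0 units", 90% power, "a two-sided alpha level of 0.05" and a correlation of one between three repeated measurements. It concludes that "a minimum of 22 patients per comparison group is required". It then states that "35 patients per group will be enrolled", giving two reasons for the increase: loss to follow-up and confounding. It multiplies 35 by four and reports 150.

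Sections 8.1, 9.1 and 10 describe how the four groups arise. The baseline CPM test places each patient in the optimal or sub-optimal class, and the pharmacy then randomises 1:1 within each class. The patients invited are "All consecutive female patients who come to the Shriners Hospital for Children" and who meet the eligibility criteria. None of these sections sets a quota or cap by class, an expected class split, or the CPM value that separates the classes.

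Section 4 has the only CPM distribution, from an earlier study of healthy people without pain: "Approximately half (42%) of the healthy subjects had a pain reduction of 10% (minimal clinical change) or more". It adds: "Poor CPM, or lack of reduction in pain during the presence of the conditioning stimuli was reported in patients with various chronic pain disorders".

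Section 16.5 lists two comparisons: (1) sub-optimal placebo against optimal placebo, and (2) clonidine against placebo within the sub-optimal class. Section 16.4 refers to three comparison schemes, but the third is not described.

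**The concern.** Section 16.3 treats the four groups as if the investigators could set all their sizes. They can set the split between arms within a class. The split between classes is whatever consecutive patients turn out to be. Four groups of 35 follow from 140 patients only if half of them are optimal, and the plan neither assumes nor enforces this.

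The optimal placebo group is the reference for comparison 1, which bears on the primary objective in section 6 (whether preoperative QST identifies patients who will have high pain). If that group is small, comparison 1 loses precision while comparison 2 gains it, so a single 90% figure cannot describe both. There are grounds in the protocol for expecting an optimal share below 42%. That figure comes from pain-free people, section 4 links poor CPM to chronic pain, and section 8.2 has patients approached once back pain is confirmed. None of this gives a number for the share in this cohort.

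**Working it through.** **Inputs.** From section 16.3: difference 2, SD 2.0 (standardised difference d = 1), two-sided alpha 0.05, power 90%, correlation 1, 22 per group required, 35 per group enrolled, total given as 150. Because 35 x 4 = 140, both totals are used. From section 10: 1:1 within class. From section 4: 42%, used as an assumed optimal share. Shares of 30% and 20% are further assumptions with no source in the documents. No loss rate is stated. I use 20% as an illustration and 37% as the upper reading, in which the whole step from 35 to 22 is loss: 1 - 22/35 = 0.37.

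**The plan's own figure.** n per group = 2 x (1.960 + 1.282)² x (2.0/2)² = 21.01, rounded up to 22. The repeated-measures factor (1 + (m - 1) x rho)/m equals 1 at rho = 1, so it changes nothing. The noncentral t gives 90.0% power for 22 against 22. The stated minimum is reproduced.

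**Enrolled sizes at a 42% share.** Optimal per arm = N x 0.42/2; sub-optimal per arm = N x 0.58/2.
- N = 150: 31.5 and 43.5.
- N = 140: 29.4 and 40.6.

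Thirty-five per optimal arm needs 70 optimal patients, hence about 70/0.42 = 167 enrolled. The binomial chance of 70 or more is 14% at N = 150 and 3% at N = 140.

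**Loss that takes an optimal arm below 22 at a 42% share.** 1 - 22/31.5 = 30% (N = 150); 1 - 22/29.4 = 25% (N = 140). At 20% loss the optimal arms keep 25.2 and 23.5.

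**Power.** Two-sample noncentral t, noncentrality = 1/√(1/n1 + 1/n2), n1 + n2 - 2 degrees of freedom, six-month outcome only. Example for comparison 1 at N = 150, 42% share, 37% loss: n = 43.5 x 22/35 = 27.3 and 31.5 x 22/35 = 19.8; noncentrality 3.39; power 91.2%.

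Results at N = 150, with 20% loss first and 37% loss second:

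| Optimal share | Comparison 1 | Comparison 2 | Clonidine vs placebo within optimal (not listed in 16.5) |
|---|---|---|---|
| 42% | 96.4%, 91.2% | 98.4%, 95.2% | 93.6%, 86.5% |
| 30% | 93.7%, 86.8% | 99.5%, 97.9% | 83.0%, 72.6% |
| 20% | 86.1%, 76.7% | 99.8%, 99.0% | 64.9%, 53.5% |

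At N = 140, a 42% share and 37% loss, comparison 1 is 89.2% and comparison 2 is 93.8%.

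**The case against.** The strongest reply is that 35 per group is a target with a wide margin, and that the listed comparisons do not suffer at the one share the documents offer. This largely stands. Twenty-two per group is the solution for equal groups. A cell below 22 is not a power failure when its comparator is larger, and at N = 150 both listed comparisons stay above 90% at a 42% share even with 37% loss.

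A reader might go further and infer that the plan's own figures leave about 20 patients per optimal arm, under the required 22. The documents do not support that. The arithmetic (31.5 x 22/35 = 19.8) treats the entire increase from 22 to 35 as expected loss, whereas section 16.3 gives confounding as a second reason and states no loss rate. It also treats 42% as this trial's expected split, although the figure comes from healthy subjects at a 10% reduction that the plan nowhere adopts as its cut-off.

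The within-optimal treatment contrast loses most, but section 16.5 does not list it, and nothing shows that it is the third scheme mentioned in section 16.4.

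What the reply does not answer is that the stated group size is not a property of the design, and that power for comparison 1 depends on a class share that the plan leaves unstated.

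**Conclusion.** The point holds as a correction to a stated figure, not as a finding that the trial is underpowered. Section 16.3 cannot promise 35 per group. At a 42% share the expected enrolment is about 31 per optimal arm and 43 per sub-optimal arm (N = 150), or 29 and 41 (N = 140). At N = 150, comparison 1 drops below the planned 90% in the scenarios examined only when the optimal share is lower than 42%: at 30% with heavy loss, and at 20% with either loss rate. At N = 140 it is marginally below 90% at 42% with 37% loss. Comparison 2 stays above 90% throughout.

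These results rest on the plan's difference and SD, an unadjusted two-group comparison at six months, and assumed shares and loss rates. The mismatch between 35 x 4 and 150 is a separate slip, and the point holds under either total.

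**What to change.** In section 16.3, replace the uniform 35 per group with expected enrolment by CPM class and arm, naming the assumed optimal share and its source. Give power separately for each comparison listed in section 16.5, over an optimal share of about 20% to 50% and a stated range of loss, with both labelled as assumptions. The CPM cut-off that defines the classes has to be stated for any expected split to mean something. The text should not say which cells will or will not retain 22 completers, since that would write an assumed loss rate into the plan.

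A look at the class split pooled over treatment at mid-recruitment is optional. It reveals nothing about treatment and need not go through the DSMB, for which section 15.1 sets no review schedule.

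The cost is a rewrite of one paragraph and some less favourable power figures. No extra patients are needed.

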4.1 CLINICAL DATA CLONIDINE

Prior relevant randomized trials, as well as a Cochrane review in 2014, have been published illustrating the benefits of Clonidine as an adjunct to preoperative analgesia. When combined with local anesthetics, intrathecal Clonidine prolongs the regression of the sensory block in a linear dose-dependent way. In addition, Clonidine prolongs the time to the first request of an analgesic with weak evidence of dose-responsiveness. Spinal Clonidine was more potent than intrathecal bupivacaine in the reduction of secondary hyperalgesia in patients recovering from abdominal surgery [45]. Perioperative systemic alpha-2 agonists (including oral Clonidine) decrease postoperative opioid consumption, pain intensity, and nausea without prolonged recovery times in adults [46]. Sixty-six patients undergoing lumbar spinal decompression where

randomized to epidural Clonidine infusion versus a placebo. There was a marked satisfactory analgesic and reduction of PCA morphine by approximately 43% over the first 36 h. Epidural Clonidine produces few side effects of its own (mean reduction of heart rate 11%–17%, and 8%–12% of arterial blood pressure compared with placebo) [47].

There is an enormous experience on the use of epidural and spinal Clonidine in pediatric population around the world. A positive effect of adjunct Clonidine was first reported by Jamali et al. in 1994 [48]. Since then, a large number of clinical studies have been published regarding the use of Clonidine as an adjunct to caudal blockade in children including structured reviews/meta-analysis and in 2014 Cochrane review specifically on Clonidine in children. They concluded that “Oral dose of 4 µg/kg, Clonidine may have reduced analgesia requirements after surgery with no significant side effects of Clonidine that were reported such as severe hypotension, bradycardia, or excessive sedation requiring intervention” [44]. There is no need to combine spinal morphine and spinal Clonidine because “it appears that the addition of intrathecal Clonidine to intrathecal morphine provides only very small clinical benefits in addition to those given by intrathecal morphine alone, especially when balanced with the increased frequency of hypotension [49].

Alpha-2 adrenoceptor agonists currently represent the most versatile and well-tolerated adjunct for the neuroaxial blockade in children. Preservative-free morphine may be indicated in certain situations, but the risk for respiratory depression and other disturbing side-effects must be taken into account [50].

5 RATIONAL AND RISKS/BENEFITS

5.1 BENEFITS

The first goal of this proposal is to determine if quantitative sensory testing (QST) assessing pain modulation can be used as a clinical tool to optimize perioperative pain management. The central hypothesis is that by identifying patients with poor endogenous inhibitory pain pathways, we will be able to personalize the patient's peri-operative therapeutic approach to optimize pain management by adding an alpha-2 adrenoceptor agonist already identified to improve peri-operative pain management. If successful, the patient will experience less post-operative pain, require less post-operative narcotics, and thus have fewer side effects. In addition, we believe by adding an alpha-2 adrenoceptor agonist, less patients will develop chronic post-operative pain.

5.2 QUANTIFIABLE RISKS

The following risks may be encountered in our patients.

QST: Subjects may suffer mild discomfort to their arm or test site, and potentially have slight bleeding and/or bruising at the blood draw site. It is also possible that some subjects may experience light-headedness or temporary malaise. There is no potential for injury during the QST assessment as the subject can control and stop the testing during the thermal test and mechanical test should he or she feel the stimulus is painful.

Clonidine: After close analysis, we believe that our treatment arm places patients at minimal risk. The most common side effects of this alpha-2 adrenoceptor agonist are: hypotension, bradycardia, and sedation. Such complications are thought to be dose-dependent. In our study we will be using low dose Clonidine which we believe will mitigate the occurrence of these. Intrathecal Clonidine, in combination with intrathecal local anesthetics or morphine, has been associated in a dose-dependent relationship to induce hypotension, bradycardia, and sedation. Almost one-third of adults receiving intrathecal Clonidine (15 to 150 mcg) and local anesthetics presented at least one episode of arterial hypotension (RR 1.81; 95% CI 1.44-2.28; NNH 8) [51]. However, intrathecal Clonidine 1ug/kg in adjunction to bupivacaine in spinal anesthesia in adolescents undergoing orthopedic surgery was not associated with hypotension or bradycardia [52]. In our study will we not be using a combination of intrathecal analgesia, minimizing the risk of side effect of hypotension, bradycardia, and sedation.

Many studies reported minor sedation after Clonidine in children, which was more severe and associated with cardiovascular side effects at higher doses (5 μ g/kg) [53]. Case reports of side effects of apnea, oxygen desaturation, and bradycardia have been reported in neonates given doses of caudal Clonidine (1.25–2.2 mg/kg) that are tolerated by older children [54-56]. Systemic Clonidine increased the risk of Intra- and postoperative arterial hypotension. However, the clinical relevance of these hemodynamic effects remains uncertain because none of the trials reported on significant adverse outcomes, such as (adult) patients (analyzed in a recent metanalysis) needing prolonged hemodynamic support with catecholamines [46].

Clonidine intrathecally has even been used and tested in mothers undergoing elective C-Sections with no additional risk. Intrathecal Clonidine 150 mcg combined with bupivacaine had a postoperative antihyperalgesic effect expressed as a significant reduction in the extent and incidence of peri-incisional punctate mechanical hyperalgesia at 48 h after elective cesarean delivery compared with intrathecal bupivacaine-sufentanil and intrathecal Clonidine 75 mcg - bupivacaine-sufentanil [57].

Specific testing as to efficacy and side effects of intrathecal Clonidine have been published. The intrathecal injection of low-dose Clonidine in healthy women resulted in dose-dependent and segmental analgesic effects. The heat pain tolerance of young women increased by 18C after 50 mcg of intrathecal Clonidine and 5 mg of intrathecal bupivacaine. This effect is similar to the analgesic effect of 5 mg epidural morphine or 30 mg epidural fentanyl in previous studies using this experimental heat pain model. Administration of Bupivacaine but not Clonidine resulted in a significant dose-related decrease in HR, but neither drug caused dose-related sympatholytic effects in the doses used [58].

Cao JP & al published in 2011, a RCT of fifty-nine children aged 6–8 year undergoing orthopedic surgery [59]. Patients were randomized to 3 groups: group B (intrathecal 0.5% bupivacaine 0.2–0.4 mg/kg and intravenous placebo); group BCit (intrathecal 0.5% bupivacaine 0.2–0.4 mg/kg plus 1 ug/kg intrathecal Clonidine and intravenous 2 ml saline); and group BCiv (0.5% bupivacaine 0.2–0.4 mg/kg) and intravenous 1 ug/kg Clonidine in 2 ml of saline. The requirements of propofol, time to first rescue analgesia, and postoperative pain or sedation scores were assessed. The duration of motor and sensory blocks and perioperative adverse drug reactions were determined. They found that Clonidine significantly prolonged the time to first rescue analgesia and reduced the requirements of propofol sedation whether administered intravenously or intrathecally. The mean Children and Infants Postoperative Pain Scale scores of children were significantly lower in

Table 3 Perioperative adverse events

	Group B (n = 19)	Group BCit (n = 19)	Group BCiv (n = 19)
Hypotension	3 (16)	5 (26)	5 (26)
Bradycardia	2 (11)	3 (16)	4 (21)
Nausea/Vomiting	1 (5)	2 (11)	1 (5)
Urinary retention	1 (5)	2 (11)	1 (5)
Shivering	2 (11)	1 (5)	0

Data are number of cases (%). Group B, intrathecal bupivacaine; Group BCit, intrathecal bupivacaine plus clonidine; Group BCiv, intrathecal bupivacaine plus intravenous clonidine. There were no significant differences between the groups.

groups BCit and BCiv than in group B. Postoperative sedation scores were higher in groups BCit and BCiv than in group B. Intrathecal Clonidine significantly prolonged the time to regression of the sensory block and recovery of motor block. There were no significant differences among the three groups regarding the incidence of perioperative adverse drug reactions.

The most recent Cochrane review conclude that despite heterogeneity between trials, Clonidine premedication in an adequate dosage (4 µg/kg) was likely to have a beneficial effect on postoperative pain in children. Side effects were minimal, but some of the studies used atropine prophylactically with the intention of preventing bradycardia and hypotension.

To further mitigate the risk associated with the use of Clonidine, the administration of the medication will only be done while patients are in well monitored setting. The intrathecal administration will be done post-operatively with optimal continuous hemodynamique monitoring, as well as the Oral dose will be administered while patient are in Hospital having hemodynamique monitoring every 8 hrs. If required, atropine will be available in the operating room and the ward.

Women or girls of childbearing potential should not get pregnant prior to their surgery nor after. The stress of surgery, the general anesthetic and the effect of different medication including clonidine may alter the natural development of a new born. You should use a proven birth control method (such as Contraceptive Pill, a diaphragm) or abstain from having sex for the 6 months that you are taking part in the study.

